#### 13.5.3 Planned Sensitivity Analyses for Secondary Endpoints

As a supportive analysis for the first secondary endpoint (centralized, blinded provider-completed mRISRAS scores), the van Elteren statistic, which is an extension to the Wilcoxon rank-sum test that accounts for the stratification factors, will be calculated.

A sensitivity analysis is planned for the second and third secondary endpoints in order to assess the robustness of the results in the presence of potential confounding variables such as reconstructed breast size, separation, and modality of boost. Further sensitivity analyses for the second and third secondary endpoints will comprise subgroup analyses to ascertain whether the effect of Mepitel Film remains clinically robust according to various categories of topical products (e.g. aqueous creams, petroleum ointments, etc.) used on the existing institutional standard of care arm.

# 13.6 Statement for Exploratory Endpoints

# 13.6.1 Exploratory Endpoints

There are several exploratory endpoints that will be evaluated in an explorative fashion:

1. In patients who undergo breast reconstruction: Reconstruction complications within 24 months post-radiation therapy, defined as wound dehiscence, wound infection requiring the administration of oral or IV antibiotics, mastectomy skin

- flap necrosis, reconstructive flap necrosis not resulting in complete loss of flap, capsular contracture, or implant leakage/rupture/deflation.
- 2. In patients who undergo breast reconstruction: Reconstruction failure within 24 months post-radiation therapy, defined as loss of autologous reconstruction/flap, implant explantation, or unplanned expander removal without immediate replacement.
- 3. Patient-reported itching, radiation skin reaction, pain, and breast swelling and tenderness as measured by the PRO-CTCAE.
- 4. The serially measured non-blinded patient- and provider-completed mRISRAS scores obtained at 6-months, 1-year, and 2-years post-radiation therapy.
- 5. In patients who receive the Mepitel Film: Serially collected response items from the Thin Film Clinical Utilization Survey.
- 6. Psychometric testing of the mRISRAS as outlined in Section 11.4.

# 13.6.2 Analysis Plan for Exploratory Endpoints

We anticipate that 30-50% of the 192 patients randomized will undergo breast reconstruction (a stratification factor at the time of randomization). Within this subset of patients, the estimated proportion of patients who experience reconstruction complications within 24 months post-radiation therapy will be reported according to arm along with the corresponding 95% confidence interval. Further, a between-arm comparison of the proportion of patients experiencing reconstruction complications within 24 months post-radiation therapy using the Fisher's exact test will be made. For this analysis, patients who terminate the study early and do not experience reconstruction complications prior to the time of early termination will conservatively be considered as having experienced reconstruction complications within the 24 months post-radiation therapy; it is expected that the number of patients terminating the study early will be low and balanced across arms. In a similar fashion, a between-arm comparison of the proportion of patients experiencing reconstruction failure within 24 months post-radiation therapy using the Fisher's exact test will be made.

As a supplemental analysis within the subset of patients who undergo breast reconstruction, a cumulative incidence function will be applied to the time to first reconstruction complication, defined as the length of time from the date of random assignment to the first reconstruction complication. Death and disease recurrence will be treated as competing events. Specifically, a cumulative incidence function will be used to estimate the percentage of patients who experienced a reconstruction complication within each arm, treating death and disease recurrence as competing risks. Between-arm differences in the cumulative incidence functions will be tested for statistical significance using the procedure of Gray. Furthermore, a cumulative incidence function regression model of Fine and Gray vill be used for multiple regression analyses; covariates included in the model will be the stratification factors and any potential confounding variables. The supplemental analyses described herein will also be applied to time to reconstruction failure.

To determine the frequency and severity of patient-reported itching, radiation skin reaction, pain, and breast swelling and tenderness, as measured by the PRO-CTCAE, the maximum grade for each of these events will be recorded for each patient and frequency tables will be generated. The descriptive analysis of the PRO-CTCAE endpoints will be based on the

safety population, defined as all patients who initiated radiation; further the safety endpoints will be analyzed according to the intervention actually received.

To determine the long-term severity of radiation dermatitis, the serially measured combined patient- and provider-completed mRISRAS scores obtained at 6-months, 1-year, and 2-years post-radiation therapy, will be descriptively summarized within each arm. These analyses are intended to complement and further contextualize the analyses related to chronic skin toxicity.

Lastly, descriptive summaries of the response items captured by the Thin Film Clinical Utilization Survey (Appendix VIII) will be tabulated for the patients who receive the Mepitel Film.

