### 2.3 Exploratory objectives

- **2.3.1** To determine the ability of Mepitel Film to decrease the rate of reconstruction complications.
- 2.3.2 To determine the ability of Mepitel Film to decrease the rate of reconstruction failure.
- **2.3.3** To determine the number of Mepitel Film changes required during treatment, evaluate ease of use from a nursing perspective, and estimate financial cost of the intervention.
- **2.3.4** To determine the frequency and severity of patient-reported itching, radiation skin reaction, pain, and breast swelling and tenderness.
- **2.3.5** To determine the long-term severity of radiation dermatitis, as measured by the combined patient- and provider-completed mRISRAS scores obtained at 6-months, 1-year, and 2-years post-radiation therapy.
- **2.3.6** To conduct psychometric testing of the mRISRAS.

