#### 13.0 STATISTICAL CONSIDERATIONS

# 13.1 Study Design

This is a randomized, controlled clinical trial to determine the ability of Mepitel Film to reduce the severity of radiation dermatitis in patients undergoing post-mastectomy radiotherapy for breast cancer when compared with the existing institutional standard of care. Patients will be randomized in a 2:1 ratio to receive either Mepitel Film or the existing institutional standard of care. The 2:1 randomization favoring Mepitel Film was chosen to aid in recruitment given an expected enthusiasm for Mepitel Film based on previously published series. Randomization will be stratified on the basis of a breast reconstruction (yes; no), planned boost (yes; no), planned bolus (yes; no), and according to 3 levels of BMI, consistent with the established cut-offs as defined by the WHO (< 25; 25-29.99; and  $\ge 30$ ).

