the date of random assignment to the first instance of such an event; death will be treated as a competing event. A cumulative incidence function will be used to estimate the percentage of patients who experienced a local and/or regional failure within each arm at 6, 12, 24, 36, 48 and 60 months, treating death as a competing risk. Between-arm differences in the cumulative incidence functions will be tested for statistical significance using the procedure of Gray. Furthermore, a cumulative incidence function regression model of Fine and Gray will be used for multiple regression analyses; covariates included in the model will be the stratification factors and any potential confounding variables. Additionally, we will descriptively summarize the proportion of patients on each arm who experienced a locoregional recurrence by study month 60.

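### Counting event-free early terminations as reconstruction complications is conservative if terminations balance as proportions, but can favour the film if they balance as counts under 2:1 allocation

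*Combined protocol and SAP*

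**What the plan says.** Objective 2.3.1 is "To determine the ability of Mepitel Film to decrease the rate of reconstruction complications". Section 13.6.2 expects 30-50% of the 192 patients to have reconstruction. It reports the 24-month complication proportion per arm with a 95% confidence interval and compares arms with Fisher's exact test. Patients who end the study early without a complication "will conservatively be considered as having experienced reconstruction complications within the 24 months post-radiation therapy", and "it is expected that the number of patients terminating the study early will be low and balanced across arms". Reconstruction failure is to be compared in a similar way, without stating whether the imputation carries over.

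Section 13.1 sets the allocation: "Patients will be randomized in a 2:1 ratio to receive either Mepitel Film or the existing institutional standard of care". Reconstruction is a stratification factor (Section 4.6), so the subset should also split about 2:1.

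As a supplement, "a cumulative incidence function will be applied to the time to first reconstruction complication", with the clock starting at random assignment, death and disease recurrence as competing events, and Gray's test between arms. "The supplemental analyses described herein will also be applied to time to reconstruction failure". No read-out month is given for these curves, whereas Section 13.5.2 reads local-regional failure "within each arm at 6, 12, 24, 36, 48 and 60 months".

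**The concern.** The rule is applied to both arms, so its effect on the comparison depends on how the terminations divide. It adds to each arm's rate in proportion to the share of that arm who leave event-free. Equal shares dilute a true difference. A larger share in the control arm pushes the comparison toward the film, which is the direction the objective hopes to show.

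The sentence offered in support speaks of the number of patients. In a 2:1 trial, equal numbers and equal proportions are different conditions, and they move the comparison in different directions. At stake is whether a film-favouring Fisher result can be read as having survived a conservative rule, and whether the per-arm percentages can be read as complication rates.

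**Working it through.** **Inputs from the documents.** Allocation is 2:1 (Section 13.1). The subset is 0.30 × 192 ≈ 58 to 0.50 × 192 = 96 patients, so about 38:20 or 39:19 up to 64:32 (film:control). Section 13.6.2 states no power, complication rate or termination rate for this endpoint, so there is no planned figure to reproduce.

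**Assumptions.** Fisher's test is two-sided at 0.05, since the plan gives no level here. The complication rate is 30% in both arms under the null and 15% vs 35% under a benefit. Terminations are unrelated to outcome. Rejection probabilities come from full enumeration of the tables.

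**Formula.** If a share d of an arm with true rate p terminates early, the reported rate is q = p + (1-p)d. The reported difference, control minus film, is

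(p_c - p_f) + (1-p_c)d_c - (1-p_f)d_f.

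**Case 1: equal proportions.** With d_c = d_f = d the difference becomes (p_c - p_f)(1-d).
- At d = 5%, 15% becomes 0.15 + 0.85 × 0.05 = 19.25% and 35% becomes 0.35 + 0.65 × 0.05 = 38.25%. The gap is 19 points instead of 20.
- Power at 64:32 is 55% with no terminations, 51% at d = 2%, 46% at 5% and 39% at 10%. At 38:20 it is 34%, 32%, 28% and 24%. Some of this loss would occur under any method once patients leave.
- Under the null, 8 film and 4 control terminations at 64:32 give film-favouring rejection of 1.2%, below the 1.9% with none.

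**Case 2: equal counts k per arm.** Now d_c = k/32 and d_f = k/64, a ratio of 2. Under a null of 30% the false gap is 0.7 × (k/32 - k/64).

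| k per arm | Reported film vs control | False gap (points) | Film-favouring rejection | Total rejection |
|---|---|---|---|---|
| 0 | 30.0% vs 30.0% | 0 | 1.9% | 3.8% |
| 2 | 32.2% vs 34.4% | 2.2 | 2.7% | 3.4% |
| 4 | 34.4% vs 38.8% | 4.4 | 3.9% | 4.1% |
| 6 | 36.6% vs 43.1% | 6.6 | 5.4% | 5.5% |

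The nominal film-favouring level is 2.5%. These rows take the counts as exactly equal. If the counts are equal only in expectation, film-favouring rejection is 3.4%, 5.5% and 8.1% and total rejection 4.5%, 6.1% and 8.4%; realised counts then need not be equal. With exactly 4 per arm in the smaller subset, total rejection is 3.0% (38:20) or 3.9% (39:19).

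**With a true benefit.** From the formula, the difference widens only if d_c/d_f exceeds (1-p_f)/(1-p_c). For 15% vs 35% that is 0.85/0.65 = 1.31. Equal counts give 2, so 4 per arm at 64:32 reports 20.3% vs 43.1%, a gap of 22.8 points instead of 20.

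**One table.** At 64:32, suppose 12 film and 10 control events are observed (18.8% vs 31.3%, p = 0.20). Adding 5 imputed events per arm gives 26.6% vs 46.9%, p = 0.066. Adding 10 and 5, which are equal proportions, gives 34.4% vs 46.9%, p = 0.27.

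**The case against.** The best defence is that balanced should be read as proportional. Section 13.2 speaks of arm balance under a 2:1 scheme, where equal counts cannot be meant. On that reading the rule dilutes a benefit, as the plan says. This stands as a reason not to claim that the plan's own expectation defeats its rule, a conclusion a reader might draw from the word number together with 2:1 allocation. The text does not settle the meaning, and on the proportional reading the reported percentages are still inflated as estimates.

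A reader might also infer that control patients will leave more often, because "The 2:1 randomization favoring Mepitel Film was chosen to aid in recruitment given an expected enthusiasm for Mepitel Film". That sentence explains the allocation ratio and predicts nothing about departures over 24 months. The documents also give film-side reasons to stop the film: intolerance in under 10% (Section 7.2.2) and 4 of 33 discontinuations in the pilot (Appendix I). Stopping the film for toxicity does not by itself end follow-up for patients willing to continue (Section 12.3.2). The direction is unknown.

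Third, the plan expects few terminations, and 4 per arm at 64:32 is already 12.5% of controls. That stands: at exactly 2 per arm, film-favouring rejection is 2.7% against a nominal 2.5%.

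Finally, the supplemental cumulative incidence analysis imputes no events, so a discrepancy would be visible. That limits the harm, but the imputed Fisher test remains the main comparison. The imputation analyses in Section 13.7 are described for mRISRAS data, and no alternative handling is stated for this endpoint.

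**Conclusion.** The concern holds in conditional form and is minor. The conservative label is justified for the superiority comparison when terminations balance as proportions. It is not justified when they balance as counts: under no true effect the comparison then leans toward the film. Under a true benefit, a higher control proportion alone is not enough to exaggerate it; the ratio of proportions must pass the break-even value. On either reading the main comparison mixes complications with departures.

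The stronger inference, that the rule breaks the 5% error rate, is not supported at the low counts the plan expects: with exactly equal counts at 64:32, total error stays below 5% at 2 and 4 per arm and passes it at 6. All sizes rest on assumed complication and termination rates and an assumed two-sided 5% test. The endpoint is exploratory (Section 13.6.1) and outside the gatekeeping sequence (Section 13.5.2), so no confirmatory claim depends on it.

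**What to change.** - Make cumulative incidence by arm with Gray's test the main analysis for complications and for failure. Censor event-free withdrawals at their last assessment, and keep death and disease recurrence as competing events.
- State a read-out that matches 24 months post-radiation, or start the clock at the end of radiation.
- Keep the count-as-event Fisher test as a labelled sensitivity analysis. Add one that imputes events in the film arm only; this is conservative for a film benefit however terminations split.
- Report early terminations and imputed patients by arm, as counts and as proportions, and say which of the two balanced refers to.
- State whether the imputation applies to the per-arm proportions and intervals and to reconstruction failure.

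The cost is SAP wording: the curves and the test are already planned for both endpoints and no new data are needed. The downside is that censoring assumes uninformative withdrawal and recurrence becomes a competing event in the main analysis. The sensitivity analyses address the withdrawal assumption; the treatment of recurrence is a change in what is estimated and should be stated as such.

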# 13.7 Missing Data

Baseline patient/disease characteristics will be evaluated between randomized patients who do not provide any patient-completed mRISRAS data with randomized patients who do provide at least one patient-completed mRISRAS score and therefore part of the full analysis set. As described in Section 13.4.2, the primary analysis uses a likelihood method to compare the prevention of radiation-induced dermatitis between the two prophylactic methods and, therefore, allows for missing mRISRAS scores under the reasonable assumption of missing at random. It is anticipated that partially completed mRISRAS questions completed by the patient will be infrequent. In the event that a patient completes  $\leq 2$  of the 4 individual mRISRAS questions, the corresponding patient-completed mRISRAS score will remain missing; however, if a patient completes 3 of the 4 individual questions (i.e. more than half of the questions), then the patientcompleted mRISRAS score will be the average of the 3 scores multiplied by 4. The amount of missing data in Alliance clinical trials, especially with respect to PROs, have been minimized, typically less than 5%, due to a long history of targeted approaches. In the event that the proportion of missing patient information is larger than 5%, we will examine the missingness mechanism by modeling indicators of missing values as a function of baseline patient characteristics, observed outcomes, and missingness of outcomes. Based on this diagnostic exercise, we will determine whether we can enhance the analyses by incorporating certain covariates or whether we need to explore more advanced methods. As sensitivity analyses, however, we will apply a recently developed macro which uses 20 different imputation approaches to missing data that was developed by the Alliance Statistics and Data Center. This approach involves the production of imputed datasets that are subsequently re-analyzed alongside the initial data, and compare the results across the spectrum of approaches to assess the veracity of the initial findings. 

# 13.8 Study Monitoring

# 13.8.1 Data and Safety Monitoring Board

This study will be monitored by the Alliance Data and Safety Monitoring Board (DSMB), an NCI-approved functioning body, twice per year. The DSMB follows the Alliance Policies and Procedures for all randomized phase III trials. The DSMB will review administrative information, accrual, including accrual of African American and Hispanic women, adverse events, and interim analysis results. All summary findings of the DSMB will be communicated to study investigators by the Alliance.

#### 13.8.2 Data Mapping Utility (DMU)

This study has been assigned Demography monitoring.

Required submission of patient demographic data for this study will be submitted automatically via OPEN.

Note: Serious adverse events must be submitted via CTEP-AERS per protocol guidelines.

# 13.8.3 Adverse Event Stopping Rule

Throughout the course of the study, we will monitor AEs in both study arms, and may suspend accrual if patients are experiencing a large number of AEs.

Accrual will be temporarily suspended to this study if 3 or more of the first 27 patients experience any grade 3+ AEs, excluding radiation dermatitis, that the study team considers to be at least possibly related to Mepitel film (i.e. an AE with attribute specified as "possible", "probable", or "definite"), and the toxicity is higher in the Mepitel film arm (on a percentage basis). In addition, accrual will be temporarily suspended to this study if 3 or more of the first 27 patients experience grade 3+ radiation dermatitis and the percentage of patients is higher in the Mepitel film arm.

The AE stopping rule may be modified if during the course of the study, new information becomes available which suggests that such a modification is necessary, or if, after temporarily stopping accrual, the above rule is found to be overly conservative.

PRO-CTCAE is not intended for expedited reporting, real time review or safety reporting. PRO-CTCAE data are included for exploratory purposes and not currently intended for use in data safety monitoring or adverse event stopping rules.

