### 7.2 Mepitel Film/standard of care treatment

Patients will be randomized in a 2:1 ratio to receive either Mepitel Film, or the existing institutional standard of care throughout the duration of their radiation. Radiation and protocol directed skin care (standard of care vs Mepitel Film) will be conducted at the registering institution.

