# 13.9 Inclusion of Women and Minorities

This study will be available to all eligible patients, regardless of race or ethnic origin.

As African American women have been shown to demonstrate higher rates of moist desquamation, they would be expected to gain a substantial benefit from Mepitel Film.  Furthermore, as poor and Hispanic women have been shown to be more likely to receive a chest wall boost, this places them at high risk of more severe skin reactions.  As such, we will make a concerted effort to accrue 25% (or 54 of 216) of the total patients in this combined category. For that, we have a Health Disparities Committee Co-Chair on this protocol, to ensure a focused effort at achieving this important accrual goal of African American and Hispanic women. Furthermore, we will enlist NCI Community Oncology Research Program (NCORP) Principal Investigators who specialize in minority and underserved patient populations and we will activate the study at NCORP sites enriched in African American and Hispanic women receiving treatment for breast cancer.

Once our study meets its planned accrual goal, we will close it to further accrual, with the exception of accruing Hispanic and African American patients, with the plan of obtaining 25% (or 54) of the 216 total patients in this combined category. We have also included the stratification factor planned boost (yes; no) at the time of randomization to ensure balance across the arms. Within the 54 Hispanic and African American study population (due to randomization approximately 36 on Mepitel Film and 18 on institutional standard of care), we will estimate the proportion of acute grade 3+ radiation dermatitis, and skin and soft tissue fibrosis using NCI CTCAE v5.0 within each arm along with the corresponding two-sided 90% confidence interval. Assuming that the proportion of such events on the Mepitel Film arm is 10% and the proportion on the institutional standard of care arm is as low 45%, the lower bound of the two-sided 90%

confidence interval for the difference in proportions constitutes a clinically important difference (90% CI: 0.14, 0.56); furthermore, sample sizes of 18 and 36 produce a two-sided 90% confidence interval for the difference in population proportions with a width that is at most 0.42, i.e. assuming that the proportion of grade 3+ acute toxicity is 10% in the Mepitel Film arm and ranges from 45% to 70% in the institutional standard of care arm.

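### Film-toxicity suspension rule (13.8.3): the trigger of 3 in the first 27 is in effect 3 in about 18 film-exposed patients; applying it to the first 27 film recipients is a cheap improvement

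*Combined protocol and SAP*

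**What the plan says.** Section 13.8.3 has two numeric rules, each leading to a temporary suspension of accrual.

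- **Film-toxicity rule.** It applies "if 3 or more of the first 27 patients experience any grade 3+ AEs, excluding radiation dermatitis". An event counts only if it is one "that the study team considers to be at least possibly related to Mepitel film". A further condition follows: "and the toxicity is higher in the Mepitel film arm (on a percentage basis".
- **Dermatitis rule.** It applies if "3 or more of the first 27 patients experience grade 3+ radiation dermatitis and the percentage of patients is higher" in the film arm. No minimum excess is given.

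Both denominators are the first 27 patients of the trial, not the first 27 in the film arm. Section 13.1 sets the allocation: "Patients will be randomized in a 2:1 ratio to receive either Mepitel Film or the existing institutional standard of care". Section 7.2.1 prohibits Mepitel Film and other prophylactic barriers in the control arm.

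Section 13.8.3 gives no rate the rules are meant to detect, no suspension probability and no schedule of looks. It allows either rule to be modified later, for instance if it proves too conservative.

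**The concern.** A control patient who receives no film should not have an event attributed to film. The first rule therefore counts a kind of event that only about two thirds of its denominator can have. Two things follow on the literal wording. The sensitivity of the rule is that of 3 events in about 18 patients, which a reader of 3 in 27 would not see. And the comparison between arms does no work, because the control percentage is zero.

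The two rules in 13.8.3 are the only numeric adverse-event boundaries in the plan. At the 9 patients a month expected in Section 13.3, 27 patients accrue in 27/9 = 3 months, so the rules may operate before the first of the twice-yearly DSMB reviews. At stake is how likely an early excess of film-related grade 3+ events is to pause accrual.

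**Working it through.** There is no stated operating characteristic to reproduce for either rule.

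**Inputs.** Threshold 3, window 27 (13.8.3); allocation 2:1 (13.1); no film in controls (7.2.1). Expected split: 27 × 2/3 = 18 film and 27 × 1/3 = 9 control. The true film-related grade 3+ rate p is not given anywhere, so a range is shown.

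**Arm comparison.** With control events at 0, the control percentage is 0/9 = 0. Three film-arm events give 3/18 = 16.7%, which exceeds 0. Whenever the count is met, the comparison is met too. The observed trigger is thus 3/18 = 16.7% of exposed patients; 3/27 would be 11.1%.

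**Chance of suspension.** With n exposed patients,

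P(X ≥ 3) = 1 − [(1−p)^n + n·p·(1−p)^(n−1) + (n(n−1)/2)·p²·(1−p)^(n−2)].

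At p = 0.10:
- n = 18: 1 − (0.150 + 0.300 + 0.284) = 0.266
- n = 27: 1 − (0.058 + 0.174 + 0.252) = 0.515

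| True rate | 18 exposed | 27 exposed |
|---|---|---|
| 5% | 5.8% | 15.0% |
| 10% | 26.6% | 51.5% |
| 15% | 52.0% | 79.3% |
| 20% | 72.9% | 92.8% |
| 30% | 94.0% | 99.5% |

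An 80% chance of suspension needs a true rate of 22.3% with 18 exposed and 15.2% with 27. The exact split will vary: with 16 to 20 exposed, the chance at a 10% rate runs from 21.1% to 32.3%. Because the count can only grow, these figures do not depend on how often the data are checked.

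**Dermatitis rule.** Let f and c be the events in 18 film and 9 control patients. The rule fires when f + c ≥ 3 and f/18 > c/9, that is, f > 2c. Summing the two binomial distributions exactly for one look at 27 patients, with the same true rate in both arms:

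| Common rate | Chance of suspension |
|---|---|
| 3% | 1.5% |
| 5% | 5.4% |
| 10% | 21.1% |
| 15% | 34.5% |
| 20% | 41.3% |
| 30% | 44.7% |
| 45% | 44.8% |
| 70% | 43.3% |

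It passes 40% only above a common rate of about 18.7%. At 10% film versus 45% control, the rates assumed in Section 13.9 for African American and Hispanic women, it is 1.4%. These figures do depend on the look schedule: a simulation that checks after every patient (20,000 runs per rate) gives about 33% at a 10% common rate and 64% at 20%.

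Counting film-arm events alone would change nothing at 18/9. If f > 2c and f + c ≥ 3, then c = 0 requires f ≥ 3, c = 1 requires f > 2, and c ≥ 2 requires f > 4. So f ≥ 3 in every case.

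**The case against.** **The plan promises no detection rate.** A reader might infer that the rule falls short of an 11% target. Section 13.8.3 states no such target, and counting the first 27 enrolled is a legitimate choice of early window. Setting 18 beside 27 exposed patients shows mainly that more exposure yields more events. This stands: there is room for improvement, but no missed figure.

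**The redundant clause does no damage.** A reader might infer that it weakens protection. It does not; it never stops a suspension, and deleting it alone adds no safety. This also stands.

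**The clause may mean something else.** Section 9.0 asks for attribution to protocol treatment, and Section 9.2 allows attribution to radiation, film or both. If the toxicity being compared were grade 3+ events of any attribution, the comparison would not be empty. The sentence does not say so, and the only toxicity it has named is the film-attributed kind. Even on that reading the count still comes from about 18 patients, so the 18-exposed column becomes an upper limit.

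**Other safeguards exist.** Adverse events are monitored in both arms with discretion to suspend (13.8.3), the DSMB reviews them twice a year (13.8.1), and expedited reporting applies (9.3). These limit the consequence, but none supplies a numeric threshold.

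**The dermatitis rule.** A reader might infer that it is close to a coin toss whenever the arms are equal. The documents do not support that. The high control rates come from one subgroup in 13.9, where "the proportion on the institutional standard of care arm is as low 45" percent; no trial-wide control rate is given; and the one observed film rate, 3% grade 3 in the Appendix I proton pilot (n = 33), points to a range where false suspension is rare. The rule also seldom fires if film works as 13.9 assumes.

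**Conclusion.** On its literal text, the film-toxicity rule is a trigger of 3 in about 18 exposed patients with a redundant arm comparison. Against a window of 27 exposed patients, this roughly halves the chance of suspension at a true rate of 10% and lowers it by about 20 percentage points at 20% (92.8 − 72.9 = 19.9); the gap is small at 30%. The conclusion rests on an approximate 18/9 split, on no control receiving film, and on attribution being read as written. It is a low-cost improvement to an early safety screen, not an error against a stated criterion.

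The dermatitis figures are a secondary observation for the DSMB. Equal-arm suspension ranges from 5% at a 5% common rate to 41–45% at rates of 20–70%, and the plan does not say where in that range the trial population lies. No change to that rule follows from this.

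**What to change.** In Section 13.8.3:

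1. Apply the existing 3-of-27 threshold to the first 27 patients who receive film.
2. Delete the arm-comparison clause from the film-toxicity rule. If grade 3+ events of any attribution were meant, say that explicitly instead.
3. State the resulting suspension probabilities over a range of true rates (the 27-exposed column above).
4. Give the DSMB the dermatitis-rule probabilities and state when that rule is checked. Restricting its count to film-arm events is not worth doing, since the rule would be unchanged at 18/9.

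The cost is protocol wording, with no added patients or procedures. There are two downsides. At a true film-related rate of 5%, the chance of a temporary suspension rises from 6% to 15%. The window closes at about the 40th patient enrolled (27 ÷ 2/3 = 40.5, or about 4.5 months at 9 a month) instead of the 27th. The longer window does not delay action on early events: film-arm patients among the first 27 enrolled are still counted, so three events among them still trigger the rule.
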